2.4.3 Post-Infusion Monitoring

Infusion related reactions (IRR) and CRS following infusion of mAb therapy, when they do occur, manifest rapidly, with a typical onset within hours of infusion, and generally appear in the dose finding phase of studies [47, 48, 49, 50] and have not been observed in participants through Cohort 8 in Part 1. Safety profiles of similar MacroGenics-produced DART products currently in Phase 1 oncology trials show that all participants who experienced IRR/CRS became symptomatic within a 6-hour post-infusion monitoring period.

The data together suggests that a 12-hour observation period following MGD014 in Part 1 of the trial will be sufficient to ensure both the safe administration of the study drug as well as management of potential IRR. As an additional conservative measure, the first participant of

each dose cohort to receive the specified MGD014 dose level will be monitored for 24 hours following MGD014 infusion. Subsequent participants of each dose cohort of Part 1 will be monitored for 12 hours.

In Part 2, each participant will be monitored for 6 hours following the first MGD014 infusion and for 4 hours following subsequent infusions.

2.4.4 Every 2 Week Administration

For the multi-dose expansion cohort in Part 2, MGD014 at 300 mcg/kg will be administered IV Q2W for a total of three doses over 4 weeks. The Q2W administration of MGD014 is supported by the repeat-dose toxicology study in cynomolgus monkeys (Study 20093423) in which MGD014 was administered weekly for 6 weeks by 2-hour IV infusions. Simulations based on the allometric modeling of the cynomolgus monkey PK data predicts that the concentration profiles in human participants will reach steady-state between the third and fourth dosing intervals and that the accumulation factor for exposure following the last (sixth) dose will be 1.84.

3 STUDY PURPOSE AND OBJECTIVES

3.1 Primary Objective

The objective of this study is to characterize the safety and tolerability of MGD014 administered IV to PLWH maintained on suppressive ART.

3.2 Secondary Objectives

- Assessment of PK and immunogenicity (ADA) of MGD014.
- Assessment of serum cytokine levels following MGD014 administration.

3.3 Exploratory Objectives

- Explore the impact of MGD014 administration on the immunologic response to HIV.
- Explore correlations between virologic and immunologic responses to MGD014.
- Assess the ability of MGD014 to alter markers of persistent HIV-1 infection.

The results of exploratory objectives may not be included in the clinical study report (CSR) or database lock unless they represent meaningful findings.

4 STUDY DESIGN

4.1 Overview of Study Design

This is a Phase 1, single-center, open-label study of MGD014 in PLWH infection on stable ART. PLWH who began ART during either chronic HIV infection or acute HIV infection with plasma HIV RNA < 50 copies/mL for 24 months prior to screening will be consented to the study. The screening procedures and initial evaluations that follow the consent determine eligibility for study entry. Eligible participants continue their baseline ART regimens throughout the study and receive either one infusion (Part 1) or an IV infusion Q2W for a total of three infusions of 300 mcg/kg of MGD014 for 4 weeks (Part 2).

[figure not shown]
4.2 Part 1 – Dose Escalation Phase

Single Ascending Dose (Cohort 1 & 2: n= 1 to 4 participants per dose cohort; Cohorts 3- 8: n= 3 to 6 participants per dose cohort). Part 1 is a single ascending dose study with a 1+3 design for cohorts 1 and 2, and a 3+3 design with staggered accrual for cohorts 3-8, with an aim of determining the safety, PK, and pharmacodynamics (PD) of ascending doses up to either the Optimal Biologic Dose (OBD) or the maximum administered dose. *During Part 1, the OBD is identified. The OBD is defined as the MGD014 dose that does not exceed the MTD (see Section 4.2.1) and achieves either maximum RO of CD3 >95% in all participants within the dose cohort, or is at the maximum administered dose (MAD) level of 300 µg/kg.*

Part 1 has 8 unique dose cohorts: 0.1, 0.3, 1.0, 3.0, 10, 30, 100, and 300 (μ g/kg). For cohorts 1 and 2, each dose cohort will consist of 1 participant, unless a dose limiting toxicity (DLT) is encountered, which will prompt expansion of the dose cohort to an additional 3 participants (see **Section 4.2.1**). A 2-week DLT period will be observed prior to escalation of the dose to the next dose cohort level. For dose cohorts 3-8, each dose cohort will consist of 3 participants, with at least 24 hours between the dosing of each participant within the cohort. If a DLT is experienced in one of the three participants, the dose cohort will be expanded to 3 additional participants. Following infusions, the study will monitor safety parameters as well as the effects of MGD014 on clinical chemistry, hematology, serum cytokines, T-cell phenotype, CD3 RO, PK, ADA and SCA.

Figure 4

Part 1: Single Ascending Dose Phase Schema

Note: Cohort X represents any cohort number

Step 1 Screening, Eligibility and Optional Baseline Leukapheresis (Pretreatment Phase)

There are two study visits associated with Step 1. At Visit 1, participants review and sign the informed consent and complete the screening requirements. At Visit 2, eligible participants enroll and baseline research assays are collected.

Note: Participants, who consented to the optional leukapheresis procedure, may be asked to complete a leukapheresis procedure. The completion of the leukapheresis procedure may occur at or at any time after the enrollment (Visit 2) but prior to receiving their MGD014 dose. The leukapheresis procedure obtains resting CD4 T cells for determination of the baseline frequency of resting CD4 T-cell infection by QVOA.

Step 2 Treatment Phase: In the MGD014 treatment phase (infusion of DART® molecule), participants continue to take their ART and receive 1 infusion of MGD014 at a given dose level based on their assigned dose cohort. The first participants of each dose cohort are monitored for 24 hours on site following infusion; subsequent participants at the same dose level will be monitored for 12 hours on site following infusion. A minimum of 24 hours is required between each participant infusion in a dose cohort. Assessment of clinical and laboratory parameters for safety, including cytokine release, occurs after the MGD014 infusion. PK, PD, and RO data are also collected after the MGD014 infusion. A 2-week DLT period follows each dose cohort and the decision to escalate to the next dose cohort level depends on the results of the testing done during this period. Reference the study schema for Part 1 in [Figure 4](#).

Step 3 Post-treatment Phase: Participants progress to Step 3 two (2) weeks after completion of their infusion. This phase is 4 weeks in length and continues monitoring each participant for safety. Serial blood samples collected during this time will analyze the PK, PD and RO measures, and the impact on T-cell phenotype.

4.2.1 Dose Escalation Rules

Dose escalation from one dose cohort to the next dose cohort level depends upon the clinical safety profile (e.g., evaluation of AEs, VS, ECGs, and clinical laboratory parameters) of the dose administered up to and including the preceding dose cohort. Participants will not be dosed at the next higher dose level until all the safety data collected following each dose through Day 14 is reviewed by the principal investigator (PI) (or designee) in conjunction with the medical monitor and are determined to demonstrate acceptable safety and tolerability.

Dose escalation continues until the OBD is achieved, provided MTD is not exceeded. The PI (or designee) may also decide to halt dose escalation if, upon review of available RO data, the RO of CD3 is >95% in all participants within the dose cohort level, and further dose escalation is not expected to provide any additional biologic utility due to saturation of the CD3 receptor. There are three possible outcomes after the infusion of MGD014 in each dose cohort:

Scenario 1: No DLT is encountered, available data on binding to T cells shows CD3 RO is ≤ 95%. Dose escalation to next dose cohort occurs.

Scenario 2: No DLT is encountered, but available data on binding to T cells demonstrates CD3 RO is >95% in all participants at this dose level. Further dose escalation will halt, and study proceeds to Part 2, using the identified OBD dose.

Scenario 3: DLT is encountered in at least one participant. Dose cohort is expanded to an additional 3 participants. **Dosing of the first additional participant will be staggered**, so that the safety and tolerability of MGD014 is evaluated over the entire 2-week DLT in the first additional participant, at the dose in question, prior to dosing any additional participants at the same dose level.

- a. If the first additional participant does not experience a DLT during this 2-week DLT period, the 2 other additional participants can proceed to receive MGD014 at this dose level with a minimum of 24 hours between the dosing of each participant. If none of the 3 additional participants experience a DLT, dose escalation to the next dose cohort proceeds.
- b. If any of the 3 additional participants experiences a DLT (so in total ≥ 2 of the participants experience a DLT within the same dose cohort), no further participants will receive a dose at this dose level, as the maximum tolerated dose (MTD) will have been exceeded. Part 2 will proceed with the MTD (the dose preceding the dose level at which MTD was exceeded). If only 1 participant was enrolled at the prior dose level, an additional 3 participants will be enrolled at the prior dose level for evaluation of the MTD.

[figure not shown]

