4.4 Dose Limiting Toxicity

DLT will be defined based on drug-related AEs that occur during the DLT period following MGD014 administration. For Part 1, the DLT period is 2 weeks following the single MGD014 infusion. For Part 2, the DLT period is defined as the period from initial infusion of MGD014 through 2 weeks following the last IV MGD014 infusion.

The severity of all AEs will be graded according to the Division of AIDS Table for Grading the Severity of Adult and Pediatric Adverse Events, corrected Version 2.1, July 2017, which can be found on the DAIDS Regulatory Support Center Web site: <http://rsc.tech-res.com/clinical-research-sites/safety-reporting/daids-grading-tables>.

A DLT is any \geq Grade 2 drug-related AE, with the following exceptions, based on the medical judgement of PI (or designee) and medical monitor:

- Grade 2 laboratory abnormality that lasts <72 hours and is not otherwise associated with clinical complications.
- Grade 2 fatigue that lasts <7 days.

In general, for participants who experience an AE that meets criteria for a DLT, subsequent administration of the study drug to that participant should be held pending management and/or resolution of the event and assessment of attribution to the study drug.

In Part 1, if a given dose level is found to exceed the MTD, meaning that \geq 2 participants experience a DLT in a single dose cohort, Part 2 will proceed with the MTD (the dose preceding the dose level at which MTD was exceeded). If only 1 participant was enrolled at the prior dose level, an additional 3 participants will be enrolled at the prior dose level for evaluation of the MTD.

In Part 2, if \geq 2 participants experience the same DLT, subsequent administration of the study drug to any participant should be held pending review by the PI (or designee), sponsor, and independent Safety Monitoring Committee (SMC). If toxicity is unacceptable, the study will be discontinued.

All participants who discontinue study treatment or follow-up procedures should comply with end of study procedures. The sponsor or its designee must be notified about discontinuation within 24 hours of such an event.

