14.9 Cohort Analyses and Monitoring

As described in [Section 4.2.1](#), the decision to escalate doses from cohort to cohort will only occur based on consensus supporting escalation by PI (or designee) and the medical monitor. The medical monitor and the PI (or designee) will review aggregate safety data up through Day 14 from all dosed participants from the prior dose cohort.

An independent Safety Monitoring Committee (SMC) will receive monthly study progress and safety monitoring reports. Study feasibility and the achievement of study milestones will be assessed in these reports. Additionally, accrual, baseline characteristics, conduct of the study (including premature study discontinuations), any interruptions of ART, virologic failures, and all reported toxicities and events will be monitored during the study on a monthly basis. The

individual safety data will be reviewed monthly to assess relation of all reported toxicities and AEs to the study treatment. The monthly data will be shared with the SMC for review.

If at any time during the study, two or more participants experience a toxicity that is Grade 3 or higher and definitely, probably, or possibly related to study treatment (as judged by the protocol team), or two or more participants experience the same DLT that is Grade 2 or higher, then enrollment into the study will be temporarily suspended and the independent SMC will be asked to review all safety data; review the relation to study treatment of the event(s); and recommend how the study should proceed with respect to resuming enrollment and continuing study treatment.

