Appendix 1 Time and Events Schedule

Part 1	Step 1-Pre-Treatment		Step 2 – Infusion					Step 3 – Post Treatment		End of Study Visit ³
	1	2	3	4	5	6	7	8	9	
Visits										10
Visit Event	Screen	Enroll ²	Day 0	Day 1 (24 hr)	Day 2 (48 hr)	Day 7	Day 14	Day 21	Day 28	Day 42
Study Week	Within 8 weeks of Day 0	0				1	2	3	4	6
Window period			≤56 days of screen	± 5 hour	± 5 hour	±2 day	±2 day	±2 day	±2 day	±5 days
Study Drug Administration										
MGD014 Infusion ⁴			X							
Clinical Procedures										
Informed Consent ¹	X									
Collect Locator information	X									
Assign PID ⁵	X									
Enrollment/Assign SID ⁶		X								
Assign Dose Cohort ⁷			X							
Medical History ⁸	X									
Physical Exam ⁹	X									X
Vital signs ¹⁰	X	X	X	X	X	X	X	X	X	
Weight	X	X	X							
Height	X									
Review of ART treatment history ¹¹	X									
Assess Karnofsky score	X									
Directed Assessment ¹²			X	X	X	X	X	X	X	
Assess ART and ART adherence ¹³	X	X	X	X	X	X	X	X	X	
Assess venous access	X									
Concomitant Medications ¹⁴	X	X	X	X	X	X	X	X	X	
ECG ¹⁵	X		X							X
Signs, symptoms and diagnosis of illnesses and diseases ¹⁶		X	X	X	X	X	X	X	X	X
Pre-Infusion Medications and anaphylactic medications ¹⁷			X							

Part 1	Step 1-Pre-Treatment		Step 2 – Infusion					Step 3 – Post Treatment		End of Study Visit ³
	1	2	3	4	5	6	7	8	9	
Visits										10
Assess for Adverse Events		X	X	X	X	X	X	X	X	X
Post-Infusion Assessment ¹⁸			X	X	X	X	X	X	X	X
Leukapheresis Procedure (Optional) ²³		X								
Clinical Lab Procedures										
CBC with differential	X	X ²²	X	X		X		X		X
Chemistry Panel ¹⁹	X		X	X		X		X		X
Calculated Creatinine Clearance	X									
Albumin & Lipase	X									
Fasting Lipids & Triglycerides	X									X
Pregnancy test (serum) ²⁰	X									
Pregnancy test (urine/POCT) ²⁰			X							
FSH; optional for proof of menopause	X									
PT, INR and aPTT	X									
CD4/CD8	X									X
HIV-1 RNA	X									X
RPR	X									
Hepatitis B and Hepatitis C	X									
Complete Urinalysis with microscopic exam	X									X
Research Laboratory Sample Collection										
HLA		X								
Anti-Drug Antibody (ADA) ²¹			X					X	X	X
Pharmacokinetics (PK) ²¹			X	X	X	X	X	X	X	X
PD: Receptor Occupancy (RO) Measurements ²¹			X	X	X	X				
PD: Serum Cytokines ²¹			X	X	X	X				
PD: T Cell Phenotype ²¹			X	X		X				
Resting CD4 T Cell Infection by QVOA ²³		X ²³								
Single Copy Assay	X	X	X							X

Part 2	Step 1 Pre-Treatment		Step 2 – Treatment					Step 3 – Post Treatment			End of Study ³
	1	2	3	4	5	6	7	8	9	10	

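### Part 1 escalation is reviewed on safety data through Day 14, but Appendix 1 schedules no CBC or chemistry after Day 7 within that 14-day DLT period

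*Protocol*

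**What the plan says.** **The escalation review.** Protocol 4.2.1 bases escalation on the clinical safety profile ("e.g., evaluation of AEs, VS, ECGs, and clinical laboratory parameters") and withholds the next level "until all the safety data collected following each dose through Day 14 is reviewed by the principal investigator", together with the medical monitor. Section 4.2, Step 2, says that "the decision to escalate to the next dose cohort level depends on the results of the testing done during this period". Section 14.9 repeats the rule: the medical monitor and the investigator "will review aggregate safety data up through Day 14 from all dosed participants from the prior dose cohort".

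**The DLT period.** Section 4.4: "For Part 1, the DLT period is 2 weeks following the single MGD014 infusion". A DLT is a drug-related AE of Grade 2 or higher. Grade 2 laboratory abnormalities are excepted if they last under 72 hours without clinical complications, so other laboratory abnormalities can qualify.

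**The schedule.** In Appendix 1, Part 1, the rows "CBC with differential" and "Chemistry Panel" carry post-dose marks at Days 1, 7, 21 and 42. Their Day 14 cells are blank. The Day 14 visit does have vital signs, a directed assessment, AE review and a PK blood sample. The row "Window period" allows ±2 days at Days 7, 14, 21 and 28.

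**The concern.** The review is tied to a 14-day period and names laboratory parameters, but the scheduled laboratory information inside that period stops half-way. A cytopenia or chemistry change that begins in the second week and causes no symptoms would not be detected by any scheduled test before the next level, about 3-fold higher, may open.

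Two parts of the protocol show that the second week is meant to count. Section 5.3.1 treats participants who withdraw before the DLT period ends as giving too little data for escalation. Scenario 3 in 4.2.1 requires the first added participant to be evaluated over the full 2 weeks. For CBC and chemistry, even a participant who completes the period has no scheduled result from its second week.

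At stake is how far the laboratory part of the MTD/MAD conclusion can be said to rest on a 14-day observation.

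**Working it through.** **Inputs.** DLT period of 14 days (4.4); CBC and chemistry days and visit windows (Appendix 1, Part 1); dose levels 0.1, 0.3, 1.0, 3.0, 10, 30, 100 and 300 µg/kg (4.2); anticipated half-life of 8 days (4.5).

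**1. The plan's own figure.** Section 2.4.2 describes half-log steps, 10^0.5 = 3.16. Adjacent ratios are 3.0 or 3.33, so about 3-fold is right. Eight levels give seven upward steps.

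**2. Reading the rows by column.** The ten Part 1 columns are Screen, Enroll and Days 0, 1, 2, 7, 14, 21, 28 and 42.

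| Row | Marked columns |
|---|---|
| CBC | Screen, Enroll (leukapheresis only), Days 0, 1, 7, 21, 42 |
| Chemistry | Screen, Days 0, 1, 7, 21, 42 |
| PK | Days 0, 1, 2, 7, 14, 21, 28, 42 |
| ECG | Screen, Days 0, 42 |

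The Day 0 panel may be drawn up to 7 days before infusion (footnote 19) and must be reviewed before dosing (9.11). Scheduled post-dose panels inside the DLT period are therefore Days 1 and 7.

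**3. Uncovered end of the DLT period** = 14 − day of the last scheduled draw.

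| Day 7 visit held on | Days uncovered | Share of 14 |
|---|---|---|
| Day 5 | 14 − 5 = 9 | 64% |
| Day 7 | 14 − 7 = 7 | 50% |
| Day 9 | 14 − 9 = 5 | 36% |

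**4. Next draw.** 21 ± 2 gives Days 19 to 23, that is 5 to 9 days after Day 14. No permitted window brings it into the DLT period.

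**5. Staggered dosing.** With the minimum 24-hour spacing, three participants are dosed on calendar days 0, 1 and 2. When the third reaches Day 14, the first is at Day 16, still before Day 19. Slower accrual could make Day 21 results available for earlier participants, but not for the last one if the review is held at that participant's Day 14.

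**6. The 72-hour exception.** Day 1 to Day 7 is 6 × 24 = 144 hours, and the next interval is 14 days. Scheduled draws cannot show whether a Grade 2 abnormality lasted under 72 hours; an unscheduled repeat is needed.

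**7. Exposure during the gap.** Assuming simple mono-exponential decay with the 8-day half-life, the fraction remaining is 0.5^(7/8) = 0.55 at Day 7 and 0.5^(14/8) = 0.30 at Day 14.

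**8. Part 2.** The DLT period runs to 2 weeks after the last infusion: 28 + 14 = Day 42. Appendix 1, Part 2, marks chemistry at Screen and Days 0, 14, 28, 63 and 77. The Day 28 panel is an infusion-day panel, reviewed before dosing. The next scheduled chemistry is Day 63 (Day 60 at the earliest, with ±3), so none follows the third infusion within the DLT period. The Day 42 CBC is for leukapheresis only (footnote 22), which is optional.

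**The case against.** **The table itself.** The point depends on marks lying under Day 21 and not the adjacent Day 14. The Part 1 ADA row reads Days 0, 21, 28 and 42 in Appendix 1 but Days 0, 14, 28 and 42 in Appendix 2. This may be an inconsistency in the protocol or a displaced cell. If the CBC and chemistry marks belong at Day 14, the Part 1 point falls. Against that, the two rows agree with each other, and the PK, receptor occupancy, cytokine and T-cell phenotype rows match Appendix 2 by day. The doubt calls for a check of the original; it does not overturn the reading.

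**No literal contradiction.** Section 4.2.1 requires review of data collected through Day 14 and does not promise a Day 14 panel. Laboratory parameters are one of four examples. This stands: it is a gap between the review rule and the schedule.

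**Early sampling has a rationale.** The main concern is cytokine release, expected within hours (2.4.1, 2.4.3), and six weekly doses in monkeys produced no clinical pathology effects (2.2.2). This supports draws at Days 1 and 7, but does not explain a 14-day laboratory review with no scheduled panel in its second week.

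**Stronger readings that the documents do not support.** A reader might infer that half of the DLT period has no laboratory data at all. Only scheduled CBC and chemistry are missing: unscheduled tests are allowed (12.2.1), and a symptomatic abnormality could surface at the Day 14 clinical review. A reader might also infer that all eight cohorts release a higher dose; there are seven steps. Nor does any document say that the report will claim 14 days of laboratory review, and SAP 4.8.2 displays values by visit. The choice of 300 µg/kg does not rest on this gap alone: 4.2.1 uses all data up to and including the preceding cohort, so later results from lower cohorts can inform later steps, and the suspension rule in 14.9 applies at any time. Finally, not every laboratory change counts toward a DLT: Grade 1 and 2 findings are generally not AEs unless clinically significant (12.2.1).

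**Conclusion.** The point holds as a mismatch between the escalation and DLT sections and the Part 1 schedule. Nominally 7 of 14 DLT days, with a range of 5 to 9, have no scheduled CBC or chemistry, and the next draw always comes after the DLT period. What may be missed is a clinically silent abnormality arising after the Day 7 draw and not picked up by an unscheduled test. The documents give no rate for such events, so the number missed cannot be estimated. ECGs show the same pattern: they are named in 4.2.1, but after 1 hour post-infusion the next is scheduled for Day 42.

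The conclusion assumes that the Day 14 and Day 21 cells are as read here, and that the review is held once Day 14 data are in, since nothing requires waiting for Day 21. It does not show that any escalation decision was wrong.

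It would also go too far to count an abnormality first seen at Day 21 as a DLT. Its onset could lie anywhere between Days 7 and 21, and the protocol's DLT period ends at Day 14.

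**What to change.** 1. **Confirm the cells.** Check the Part 1 CBC and chemistry marks at Days 14 and 21 against the original table, and resolve the ADA difference between Appendices 1 and 2.

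2. **Reconcile, for any further Part 1 dosing.** Bring Protocol 4.2, 4.2.1, 4.4 and 14.9 into line with Appendix 1 by drawing CBC and chemistry at the existing Day 14 visit, with results included in the 4.2.1 review. The nominal uncovered period falls from 7 days to 0. Keep the Day 21 panel: moving it instead would leave 42 − 14 = 28 days without one. The cost is one added tube and assay per participant, with no new visit, because blood is already taken for PK.

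3. **For cohorts already dosed.** Sections 2.4.3 and 6.1 indicate that Cohort 8 has been dosed and the Part 2 dose chosen, so step 2 may come too late for most or all of Part 1. Add to SAP 4.4, and carry into the report, that scheduled CBC and chemistry within the Part 1 DLT period ended at Day 7. Qualify the laboratory part of the MTD/MAD conclusion accordingly. Beside it, list drug-related laboratory abnormalities of Grade 2 or higher first seen at Day 21, without reclassifying them as DLTs. This costs a few sentences and one listing from data already collected.

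4. **Part 2.** Reconcile the DLT period in 4.4, which ends at Day 42, with a schedule whose next chemistry after the Day 28 infusion-day panel is Day 63 and whose Day 42 CBC is for leukapheresis only. State the resulting laboratory coverage in the SAP.
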